### 3.4 Data Collection

#### Instrumentation

The outcomes for this proposal were chosen to inform our specific aims concerning veteran's knowledge about cognitive aging (AIM 1), psychological wellness (AIM 2), and cognitive and functional ability (AIM 3). The following measures will be used at baseline and follow-up visits to test the hypotheses associated with each aim. A detailed description of each measure is provided below. In its entirety, it will take participants an average of 2 hours to complete the following measures (see below); sessions will be broken into two one-hour sessions to minimize any fatigue. A demographic questionnaire will be administered only at baseline that captures basic data including age, gender, race, educational history, and occupational history.

AIM 1: Knowledge of Memory Aging Questionnaire-Revised (KMAQ; Cherry et al., 2003) measures laypersons' knowledge of memory changes in adulthood for research or educational purposes using true/false/"don't know" questions, with half of the questions pertaining to normal memory aging and the other half covering pathological memory deficits due to non-normative factors, such as dementia. Test-retest reliability and convergent and discriminant validity were established at adequate levels (Cherry et al., 2000).

Qualitative interview questions taken from the Healthy Brain Study (Wilcox et al., 2009) measure laypersons' perceptions and knowledge of aging brain processes regarding cognitive health promotion. Respondents answer questions based upon life experience and information provided via various media entities. These questions will provide narrative structure to veteran perceptions of memory and aging.

AIM 2: Multifactorial Memory Questionnaire (MMQ; Troyer & Rich, 2002) will be used to measure psychosocial functioning (and also functional ability for AIM 3; see below). The MMQ is a measure constructed to reflect aspects of memory that are potentially amenable to clinical intervention. The MMQ-Contentment subscale assesses emotions and perceptions about current memory ability including anxiety, embarrassment, and irritability. The scale contains 18 statements rated on a 5-point scale (strongly agree, agree, undecided, disagree, strongly disagree). The MMQ has been shown to have adequate content validity, test-re-test reliability (.86-.93), internal consistency (.83-.95) and convergent and discriminant validity. General and Memory Specific Control Beliefs Scale (Bielak et al., 2007) will be used to measure perceived control over cognitive health. The scale is composed of two sets of items focusing on general and memory-specific control beliefs. We are interested in examining changes in memory-specific control beliefs.

AIM 3: MMQ The MMQ-Ability subscale contains 20 items phrased as memory failures in everyday memory situations (e.g., forgetting an appointment). Respondents indicate the frequency with which they have made each mistake over a two-week period using a 5-point scale (all the time, often, sometimes, rarely, never). The MMQ-Strategy subscale measures the self-reported use of strategies designed to improve memory. This subscale contains 19 items describing different memory aids and strategies applicable to everyday memory tasks (e.g., writing appointments on a calendar). Respondents indicate the frequency with which each strategy was used over a two-week period using a 5-point scale (never, rarely, sometimes, often, all the time). A battery of neuropsychological measures will provide quantitative measurement of cognitive functioning and includes validated and standardized measures reflecting the cognitive domains of memory, attention, executive functioning, and language: California Verbal Learning Test – Second Edition (CVLT-II), Wechsler Memory Scale – Third Edition (Logical Memory and Visual Reproduction), Digit Span, Delis-Kaplan Executive Function System (Trail Making and Verbal Fluency). An overall score will be obtained by taking the average of the z scores for each individual test. Alzheimer's Disease Cooperative Study Global Impressions of Change Scales (ADCS-GICS; Schneider et al., 2006; Knopman et al., 1994) include self-rated and study partner-rated versions, which will be used as an index of global, real world changes in functional ability. Self rated and study partner rated versions were developed specifically for use with non-demented elderly.

### 3.5 Analysis Plan

To test the primary outcome we will run repeated measures ANOVAs with the factors of group x time. Follow-up analyses will be done as indicated.

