### 3.2 Type of Study

Prospective, randomized, no treatment control

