#### b. Study Related Procedures

- i. Bedford AgeWISE Course: The memory and aging course will take place in the building 5 solarium on the Bedford VA campus. The course will be run by neuropsychology staff under the supervision of [name] [name], a clinical neuropsychologist who has developed this manualized group, and has run the group for a number of years at the Bedford VA. Healthy older adults ages 50 to 90 will be recruited from the community at large and from advertisements on the Internet and local gathering places. Over the next year, we intend to enroll a maximum of 144 participants. Of the 144 participants, 72 of those will be older veterans, and 72 will be study partners, when study partners are identified, available, and willing to participate. Veterans without study partners will not be excluded from the study. Of the 72 veterans (with or without study partners), 36 will be assigned to the intervention group and 36 will be assigned to the control group. All veterans participating in the study will perform a standard battery of neuropsychological tests(attached). These tests will be administered in a separate study session. Veterans will be excluded if they display impairment on a cognitive screening measure, as determined using age corrected criteria (using criteria: Schretlen, Testa, and Pearlson, 2010) as follows:

Age / MMSE Cut-off

51-55 / 26 and below

56-60 / 25 and below

61-65 / 25 and below

66-70 / 25 and below

71-76 / 23 and below

76-80 / 23 and below

81-85 / 23 and below

86 + / 22 and below

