Or self or informant reported diagnosis of a brain disorder affecting cognition such as Alzheimer's disease, Mild Cognitive Impairment, Parkinson's disease, other dementia, stroke, or brain injury or diagnosis of a major mental illness such as major depression, schizophrenia, or bipolar disorder; active alcohol or substance abuse. In addition to the standard neuropsychological tests, participants will be filling out questionnaires regarding their cognition and quality of memory. Veterans with a study partner (a spouse, family member, significant other, or adult child living with the veteran) will have the study partner complete a brief interview of participant functioning on three separate occasions. Interviews will be conducted prior to the study, within two weeks after the study is completed, and again at 6-months following the previous interview. Interview questions will ask study partners to list or describe any: notable recent events; medical problems; physical abilities; any concerns the participants might have; description of the participant's thinking abilities; description of the participant's feelings or behavior; descriptions about the participant's daily activities and social activities; and any other related information regarding the participant. Veterans (intervention and control) will complete protocol measures at baseline, within 2 weeks after the intervention is completed, and again at 6-months after immediate follow-up.

Once the group is underway, a manual will be provided to each veteran. The manual will include an overview of the topic discussed during the class as well as written strategy instructions, practice exercises, and homework (e.g., readings on the week's topic, questions, and additional practice exercises on the compensatory strategy of the week). Each of the sessions will begin with veterans reviewing the past week's homework assignments. The group leader(s) will then introduce a new topic along with a compensatory strategy following a scripted set of instructions. Veterans will be encouraged to ask questions and participate in general discussion. Attached please find a copy of the 12-week course outline that describes the content of each group session.

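### The group x time repeated-measures ANOVA is valid but uses baseline only as a level of time; adjusting for baseline would give a more precise arm comparison at each follow-up, by an amount that depends on an unstated correlation

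*Combined protocol and SAP*

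**What the plan says.** Section 3.5 (Analysis Plan) has two sentences: "To test the primary outcome we will run repeated measures ANOVAs with the factors of group x time", then "Follow-up analyses will be done as indicated". Neither the section nor the rest of the document names a covariate, a covariance structure or a rule for missed visits.

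The design supplies what a baseline-adjusted analysis needs. Section 3.2 describes the study as "Prospective, randomized, no treatment control". Section 3.3 b states that "36 will be assigned to the intervention group and 36 will be assigned to the control group" and that veterans in both arms "will complete protocol measures at baseline, within 2 weeks after the intervention is completed, and again at 6-months after immediate follow-up". Section 3.4 (Instrumentation) adds: "The following measures will be used at baseline and follow-up visits to test the hypotheses associated with each aim".

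The only numerical repeatability figure is for the Multifactorial Memory Questionnaire (MMQ): "test-re-test reliability (.86-.93". No retest interval is given. No effect size, SD, alpha, power or dropout rate is stated.

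**The concern.** With baseline as a level of time, the group x time interaction compares change from baseline between arms. Under randomisation the arms have equal baseline means in expectation, so baseline need not be subtracted in full. Regressing on it, or constraining its mean to be equal across arms, removes baseline noise with the best weight instead of a fixed weight of one. The change score is therefore less precise than it need be unless r is close to 1.

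This is the only test named and there are 72 randomised veterans. The baseline scores are collected anyway, so any precision lost here could be recovered without further cost to participants.

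**Working it through.** The plan has no power figure to reproduce. Taken from the documents: n = 36 per arm and three visits (baseline, immediate, 6 months). Assumed: two-sided 5%, unit SD, equal correlation r between visits, complete data, and arm differences d1 (immediate) and d2 (6 months).

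**1. One visit, whatever the effect size.** The variance of a change score is 2(1−r). The variance after adjustment for baseline is 1−r². The ratio is (1−r²)/[2(1−r)] = (1+r)/2. The confidence interval narrows by 1−√[(1+r)/2], and the equivalent arm size is 36 ÷ [(1+r)/2].

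| r | Variance ratio | 95% CI narrower by | Equivalent n per arm |
|---|---|---|---|
| 0.5 | 0.75 | 13% | 48 |
| 0.7 | 0.85 | 8% | 42 |
| 0.86 | 0.93 | 4% | 39 |
| 0.93 | 0.965 | 2% | 37 |

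**2. Both follow-up visits together.**
- Planned ANOVA: noncentrality (n/2)·Σ(e−ē)²/(1−r), with e = (0, d1, d2), on F(2,140).
- Adjusted joint test: (n/2)·v′R⁻¹v, with v = (d1, d2) and R having diagonal 1−r² and off-diagonal r−r², on F(2,68).

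Example: lasting 0.4 SD, r = 0.5.
- ANOVA: Σ(e−ē)² = (2/3)(0.16) = 0.1067, so 18 × 0.1067/0.5 = 3.84 and power is 39.3%.
- Adjusted: v′R⁻¹v = 2(0.16)/[(1−r)(1+2r)] = 0.32, so 18 × 0.32 = 5.76 and power is 54.6%.

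Power (%), ANOVA → adjusted, for 0.4 SD at the immediate visit:

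| r | Gain lasts | Half faded at 6 months | Fully faded |
|---|---|---|---|
| 0.5 | 39 → 55 | 30 → 40 | 39 → 43 |
| 0.7 | 60 → 70 | 48 → 54 | 60 → 62 |
| 0.86 | 92 → 94 | 82 → 84 | 92 → 92 |

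At r = 0.86 and 0.4 SD, power is already high and leaves little room to rise. With a lasting 0.3 SD the same formulas give 69.1 → 72.6%. Across the quoted .86-.93 range the gain is about 0 to 4 points.

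**3. Where adjustment does not help.** These formulas leave out the small loss from chance baseline imbalance, so the unfavourable corner was simulated: exact compound symmetry and an effect at the immediate visit only. At r = 0.90 to 0.94 the adjusted unstructured test was 0.9 to 1.3 points below the ANOVA. One such cell is r = 0.93 with 0.2 SD, at 63.2 versus 62.0%.

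**4. Separating adjustment from covariance handling.** With correlations of 0.7 between adjacent visits and 0.5 from baseline to 6 months, an unadjusted multivariate test has power 48.0, 51.4 and 71.0% (lasting, half faded, faded). The adjusted test has 57.9, 55.2 and 71.5%. Adjustment itself adds about 10, 4 and under 1 point. The univariate ANOVA (49.9, 40.7 and 54.6% in simulation) also differs because it assumes sphericity.

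**5. Type I error.** In simulation under no effect, both tests rejected at about 4.8%, so the issue is efficiency and not validity.

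**The case against.** The strongest defence is that the ANOVA is conventional and valid, that section 2.3 describes the work as a pilot, and that the gain is small at the only reliability the documents quote. The gains of 9 points or more need r of about 0.5 to 0.7, which no section supports. This stands as a limit on size. It does not remove the point: .86-.93 is quoted for the MMQ alone, without a retest interval, and section 3.5 does not say which measure is primary. No single r can be taken for the knowledge questionnaire, the control-beliefs scale or the cognitive composite.

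A second objection also stands: the gain relies on baseline scores being unaffected by allocation, and the order of baseline testing and randomisation is not stated.

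A reader might infer more than the documents support:
- *That the planned test is biased or invalid.* It is neither.
- *That adjustment can never cost power, or costs only a single degree of freedom.* Step 3 shows a small loss in one corner. Against a sphericity-assuming ANOVA, the denominator degrees of freedom fall from 140 to 68, mostly because of the unstructured covariance.
- *That the plan drops veterans who miss a visit.* Classical software often does, but section 3.5 gives no rule, so any loss from a completer-only analysis cannot be charged to the plan.

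**Conclusion.** The point holds as one of efficiency. The variance ratio (1+r)/2 for a single-visit difference needs no effect size, only equal variances across visits and a baseline unaffected by allocation. The power gains are conditional on assumed effects and correlations: for a lasting 0.4 SD effect, about 15 points at r = 0.5 and 9 at r = 0.7. They shrink to about 0 to 4 points at .86-.93. The worst case is a loss of about 1 to 1.5 points, when sphericity is exact, r is about 0.9 or more and the effect is confined to one visit.

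The change is worth making, because the data are already collected and the possible gain well exceeds the possible loss. It does not correct an error.

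Two related matters are secondary and lie outside the efficiency claim. Missed visits have no stated handling. Follow-up is given as 3 and 6 months in section 2.1 but as immediate and 6-month in sections 3.3 b and 4.7, and these must be reconciled before the tested visits are fixed.

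**What to change.** For the randomised Bedford course, replace the first sentence of section 3.5 with wording to this effect:

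- Each continuous score measured at baseline is analysed with a linear mixed model on all available scores of every randomised veteran, analysed as randomised.
- The model has visit and arm x follow-up visit terms, the baseline mean constrained equal across arms (or baseline as a covariate), unstructured covariance and Kenward-Roger degrees of freedom.
- The test is the joint test of the arm differences at the follow-up visits, or the difference at one visit named in advance. Each difference is reported with its 95% CI.
- Any scale that rates change and has no baseline score is compared between arms at each follow-up. The global impression of change scales, "which will be used as an index of global, real world changes in functional ability", may be such a case; section 3.4 lists them among measures used at baseline, so this should be clarified.

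Before adopting the constraint, confirm and state that baseline testing precedes allocation or is otherwise unaffected by it.

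Cost: a wording change, fixed before outcomes are examined by arm. The joint test has 68 denominator degrees of freedom instead of the 140 of a sphericity-assuming ANOVA, with the small worst-case loss above. No extra visits or data are needed, and standard software suffices. The choice of primary outcome, multiplicity and clustering by course group are separate points that this wording does not settle.

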## 2.2 Preliminary Studies

The proposed intervention was originally designed as a clinical service to meet the needs of the large number of veterans presenting with concerns about their memory despite normal cognitive performance on formal evaluation, and then refined over a period of four years. We originally collected data using a seven-item questionnaire we felt was pertinent to the goals of the intervention (see appendix). Using a within-subjects pre-post test design with a representative sample of nine veterans (mean age=78, SD=4.2) we found a reduction in anxiety about cognitive functioning (*How concerned are you about your memory, or potential memory problems, as you get older?*;  $t(8)=2.50, p<.05$ ) and an increase in perceived knowledge about brain aging (*How much do you feel you know about what happens to your memory and your brain as you age?*;  $t(8)=3.00, p<.05$ ) at immediate follow-up as compared to baseline (Kraft & Steadman-Wood, 2008). Qualitative comments collected at the end of the intervention also supported the veterans’ view that the intervention was effective: “I was hoping to get tips about how to improve my memory and I did”, “Through the group I found that we, my wife and I, are not alone”, and “I didn’t realize there was so much to learn.”

Using a subset of the measures proposed in the current submission we recently collected within-subjects baseline and immediate follow-up pilot data (collected within two weeks from the end of the intervention) from a new group of four cognitively healthy veterans (mean age=61, SD=2.7) participating in the intervention (measures from left to right on the graph include the Knowledge of Memory Aging Questionnaire-Revised; Multifactorial Memory Questionnaire: contentment, ability, and strategy use subscales; and Memory Controllability Inventory: memory specific control beliefs subscale). Despite the small sample size, these pilot data show numerical trends, some reaching significance, in a repeated-measures ANOVA,  $F(1,6)$ , that provide support for a subset of our

predictions including improvement in knowledge of cognitive aging ( $p=.07$ ), increased contentment with memory ( $p=.03$ ), improved self- perceived memory ability ( $p=.05$ ), increased strategy use in daily life ( $p=.00$ ), and increased feelings of memory- specific ( $p=.01$ ) control.

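### The course is taught in classes but the group x time ANOVA has no class term, so false positives exceed the nominal rate wherever classmates' outcomes correlate

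*Combined protocol and SAP*

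**What the plan says.** The whole analysis plan (Section 3.5) is two sentences: for the primary outcome "we will run repeated measures ANOVAs with the factors of group x time", and "Follow-up analyses will be done as indicated". No section mentions a class or cohort term, a random effect for class, cluster-robust standard errors or an ICC.

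Section 3.2 gives the design as "Prospective, randomized, no treatment control". Section 3.3 b (Study Related Procedures) sets the allocation: "36 will be assigned to the intervention group and 36 will be assigned to the control group". The same section shows that the intervention is delivered to groups. Of the course manual it says "The manual will include an overview of the topic discussed during the class"; of the sessions, "The group leader(s) will then introduce a new topic along with a compensatory strategy following a scripted set of instructions" and "Veterans will be encouraged to ask questions and participate in general discussion". Sessions open with a review of the previous week's homework. How many classes the 36 intervention veterans form, and how large each is, is not stated.

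**The concern.** This is a partially nested design. Intervention veterans share a leader, a room and a discussion over a 12-week course; nothing in the documents groups the untreated controls. Classmates' outcomes after the course may therefore be correlated in one arm only.

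The subject term in a repeated measures ANOVA deals with correlation between visits of the same person. It does nothing about correlation between people in the same class. If that correlation is positive, the effective number of independent observations in the intervention arm is below 36. Confidence intervals are then too narrow and p-values too small, and one unusually good or poor class can pass for an intervention effect. The correlation may differ between knowledge, attitudes, strategy use and test scores, so one outcome may be affected and another not. As written, the plan would not show which.

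**Working it through.** **Inputs from the documents.** 36 veterans per arm; three visits (baseline, within two weeks after the course, six months after that); untreated controls; a group x time model.

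**Assumed, because the documents give no value.** Two-sided alpha 0.05; no dropout; equal classes (6 of 6, 4 of 9 or 3 of 12); ICC from 0 to 0.10; visit correlation 0.7, varied to 0.5 and 0.85. The plan has no power or error calculation to reproduce.

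**Step 1: standard error.** With class size m, the design effect in the intervention arm is D = 1 + (m - 1) x ICC. With unit variance, the true variance of the between-arm difference is (D + 1)/36. A test that ignores class uses, on average, a pooled variance s² = [(36 - D)/35 + 1]/2, giving 2s²/36. The ratio of the reported to the true standard error is the square root of 2s²/(D + 1). At ICC 0.05:

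- m = 6: D = 1.25, s² = 0.9964, ratio = √(1.9929/2.25) = 0.94
- m = 9: D = 1.40, s² = 0.9943, ratio = √(1.9886/2.40) = 0.91
- m = 12: D = 1.55, s² = 0.9921, ratio = √(1.9843/2.55) = 0.88

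At ICC 0.10 the ratios are 0.89, 0.84 and 0.80. For one class of 36 at ICC 0.05 (D = 2.75) the ratio is 0.72.

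**Step 2: type I error of the planned test.** The group x time F test was simulated under no intervention effect (40,000 trials per setting, compound symmetry, class effect at both follow-ups in the intervention arm only). The ICC was defined either as the class share of variance in change from baseline (change) or in the follow-up score (score). Rejection rates (%) at visit correlation 0.7:

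| ICC | Scale | 6 classes of 6 | 4 of 9 | 3 of 12 |
|---|---|---|---|---|
| 0.05 | change | 6.4 | 7.1 | 8.2 |
| 0.05 | score | 7.2 | 8.8 | 10.1 |
| 0.10 | change | 8.0 | 10.1 | 11.9 |
| 0.10 | score | 9.7 | 12.8 | 15.6 |

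At ICC 0 the rate is 5.0-5.2%; at ICC 0.02 it is 5-7%.

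**Step 3: why the scale matters.** Take the between-person variance at a visit as 1. A score ICC of 0.05 then means a class variance of 0.05/0.95 = 0.0526. Change from baseline has variance 2(1 - r) for visit correlation r, so the ICC of change is 0.0526/[0.0526 + 2(1 - r)]: 0.050 at r = 0.5, 0.081 at r = 0.7 and 0.149 at r = 0.85. The simulated rates follow this. At score ICC 0.05 they are 6.5-8.1% with r = 0.5 and 9.6-15.4% with r = 0.85. On the change scale r has no effect.

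**Step 4: does the class term repair it?** A partially nested model (random class effect in the intervention arm, Satterthwaite degrees of freedom, class variance not allowed below zero) was applied to the mean of the two follow-ups minus baseline, at ICC 0.05-0.10 on both scales. Its type I error was 4.3-5.0% with 6 classes, 4.4-5.4% with 4, 4.7-6.2% with 3, and 6.0-9.1% with 2 classes of 18.

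**The case against.** The strongest reply is that nothing in the documents shows an ICC above zero, and several features point to a small one: one site, one supervising neuropsychologist, a manual and scripted sessions. The pilot remark "Through the group I found that we, my wife and I, are not alone" does not help the concern much. It suggests that the group format is valued, which could be equally true of every class, whereas an ICC requires classes to differ. This stands, and the conclusion does not rest on that remark. But a small ICC is not a zero one, and several outcomes are self-reported attitudes and habits that discussion could move together.

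Classes may also be smaller than assumed. Nine classes of four at ICC 0.05 and visit correlation 0.7 give 5.8-6.5%, a smaller excess but still an excess.

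A class effect might fade by six months. For this F test that makes no difference: visit patterns (0, 1, 1) and (0, 1, 0) both have a centred sum of squares of 2/3. Simulating an effect at the first follow-up only gave 7.3, 8.5 and 10.2% for 6, 4 and 3 classes.

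Controls are not explicitly said to be ungrouped. Their follow-up is timed to the end of the course, so they may be assessed in waves alongside a class. That is worth clarifying, but it would not remove correlation arising inside the classes.

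Finally, Section 2.3 presents this as a pilot study, and the remedy costs power. Both points bear on priority. Neither makes the unclustered standard error correct.

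**Conclusion.** The concern holds, conditionally. Class delivery, an untreated comparator and a model without class are all in the documents, and the direction of the error is certain wherever classmates correlate positively. Its size is not, because the number of classes, their size and the ICC are all unstated. It is nil at ICC 0 and slight at 0.02. It becomes material from about 0.05, where a nominal 5% test rejects 6.4-10.1% of the time with 6 to 3 classes at visit correlation 0.7. It could be larger for an outcome with high visit correlation if the ICC applies to the score. The change should be made, with medium confidence about how much it will matter in practice.

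**What to change.** 1. State the planned number and size of classes, and plan four or more if this is still open. State also whether controls are enrolled and assessed in waves tied to a class; if so, the model needs to reflect wave in both arms.
2. Record each intervention veteran's class as a data field.
3. Pre-specify a partially nested mixed model: group, time and their interaction, a random class effect in the intervention arm only that can affect change from baseline, controls as singletons, and Satterthwaite or Kenward-Roger degrees of freedom.
4. Report the estimated class variance for each outcome.
5. State the limit in the report. With three or fewer classes the correction is only partial, and with one class no model can separate class from intervention.

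The administrative cost is one field and a few lines of text. The statistical cost is real: wider intervals and lower apparent power. For a 0.5 SD effect at ICC 0.05 and visit correlation 0.7, testing the mean of the two follow-ups minus baseline (one contrast, not the planned interaction test), adding the class term changes power as follows:

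- 6 classes: from 0.83-0.85 to 0.70-0.75
- 4 classes: from 0.82-0.84 to 0.59-0.65
- 3 classes: from 0.81-0.83 to 0.50-0.56

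Part of the higher figure in each pair comes from the inflated error rate and is not genuine power. The contrast between rows is the reason to settle the number of classes before the analysis.
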